Subjects who do not tolerate a minimum dose of 100 mg/day will be withdrawn from the study (Section 10.1.3.1 and Section 10.1.3.2).

Subjects with worsening scleroderma such as skin thickening or other scenarios will be allowed to use rescue therapy starting at or after Week 26, and those with confirmation of predicted FVC decline (after 2 separate confirmations within 4 weeks via an unscheduled visit) will be allowed to use rescue therapy starting at or after Week 16 (Section 11.3.1.2).

End of treatment (EOT) or early termination (ET) assessments will be performed for all subjects, who will undergo efficacy and safety evaluations. Efficacy evaluations will include change in

the composite score of ACR CRISS Components, [REDACTED], [REDACTED]
[REDACTED], and certain biomarkers.

[figure not shown]
Subjects who discontinue study treatment before EOT (Week 52) should be encouraged to continue in the study and complete all the required study assessments through Week 52.

If a subject decides to permanently withdraw consent from the study, every attempt should be made to have the subject complete the ET visit and complete the study assessments listed at Week 52 (Table 1).

In the event a subject does not return to the clinical site for the ET and/or safety follow-up visit, the Investigator must make every effort to contact the subject by telephone to for the collection and source documentation of safety information such as AEs, dosing compliance, and review of concomitant medications and date of last dose of study drug. Return of unused medication will be performed by courier where allowed.

A safety follow-up visit will occur at Week 56 (Visit 9) for subjects who complete the double-blind treatment period (Week 52) and 4 weeks after the last dose of study drug for subjects who ET from the study.

Further details can be found in the Study Schema (Figure 1).

a Starting daily dose will be MT-7117 300 mg QD or matching placebo, with possibility to reduce the dose in a stepwise manner from 300 mg QD to 200 mg QD and possibly from 200 mg QD to 100 mg QD to manage subjects' tolerability to study drug.

b At the discretion of the Investigator, rescue therapy may start as early as Week 16 with confirmation of predicted FVC decline, and as early as Week 26 with worsening scleroderma such as skin thickening or other scenarios.

Figure 1: Study Design Schema

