16.3.2 Data Handling

16.3.2.1 Definition of baseline for Efficacy and Safety Endpoints

Unless otherwise specified, the baseline values for the endpoints will be the latest available data obtained prior to the first administration of study drug.

16.3.2.2 Handling of Time Point Data in Analyses Performed by Measurement time Point (Analysis Visit Windows)

For the analyses performed for each measurement time point, the allowable range of data handling for the analysis will be specified as analysis visit window in the SAP.

No data imputation will be performed using data from outside the allowable range. If multiple values are available within the allowable range for the endpoint in question, then the latest and closest value of the window value will be used for analysis.

16.3.2.3 Handling of Reference Values and Indeterminate Values for Clinical Laboratory Test Parameters

If a laboratory test value or its reference is indeterminate due to a problem with the test sample, then this value will be handled as a missing value.

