7.2 Analysis Visit Definitions

Table 3 Analysis Visit Window for PtGA, PhGA, mRSS, FVC, DLco, HAQ-DI

Visit Number	Analysis Visit	Nominal day	Analysis Visit Window
1	Screening	NA	NA to -1
2	Baseline	First dose day	NA
3	Week 2	Day 15	Day 2 to 29
4	Week 6	Day 43	Day 30 to 77
5	Week 16	Day 113	Day 78 to 147
6	Week 26	Day 183	Day 148 to 228
7	Week 39	Day 274	Day 229 to 319
8	Week 52 (EOT)	Day 365	Day 320 to 379
10	Week 56 (EOS/FU)	Day 393	Day 380 to 400

Table 3 Analysis Visit Window for other than PtGA, PhGA, mRSS, FVC, DLco, HAQ-DI and pregnancy test

Visit Number	Analysis Visit	Nominal day	Analysis Visit Window
1	Screening	NA	NA to -1

2	Baseline	First dose day	NA
3	Week 2	Day 15	Day 2 to 29
4	Week 6	Day 43	Day 30 to 77
5	Week 16	Day 113	Day 78 to 147
6	Week 26	Day 183	Day 148 to 228
7	Week 39	Day 274	Day 229 to 319
8	Week 52 (EOT)	Day 365	Day 320 to 379
9	Early termination (ET)	End of treatment	End of treatment + 7
10	Week 56 (EOS/FU)	Day 393	Day 380 to 400

Table 4 Analysis Visit Window for pregnancy test

Visit Number	Analysis Visit	Nominal day	Analysis Visit Window
1	Screening	NA	NA to -1
2	Baseline	First dose day	NA
3	Week 2	Day 15	Day 2 to 29
4	Week 6	Day 43	Day 30 to 77
5	Week 16	Day 113	Day 78 to 147
6	Week 26	Day 183	Day 148 to 204
	Week 32	Day 225	Day 205 to 249
7	Week 39	Day 274	Day 250 to 294
	Week 45	Day 316	Day 295 to 340
8	Week 52 (EOT)	Day 365	Day 341 to 379
9	Early termination (ET)	End of treatment	End of treatment + 7
10	Week 56 (EOS/FU)	Day 393	Day 380 to 400

The date of the first dose of study drug is defined as Day 1.

Unless otherwise specified, the baseline value will be the last observed value of the parameter of interest prior to the first intake of study drug (this includes unscheduled visits). For FVC, %pFVC and %pDLco etc in the pulmonary function test, the baseline value will be the last observed value prior to the first intake of study drug. The data of "accepted" or "failed" generated by the centralized over read specialist will be utilized for each pulmonary function test parameters. The data accepted by the centralized over read specialist will be used if it

exists. However, when there is no accepted data available at a visit, the failed data that will be approved in BDRM will also be used.

Unless otherwise specified, no data imputation will be performed using data from outside the allowable range.

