For other visits, if there are multiple data in a window, the closest data to nominal day will be used. If the distance to the nominal day is the same, the data of later date will be used.

In the event that in a post baseline visit window there are only values from unscheduled visit, these values will be used to derive the value for this visit.

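### The SAP's efficacy visit windows have no early-termination row, so the closest-day rule normally drops a dropout's last CRISS components when the subject leaves after that window's scheduled visit

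*SAP*

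**What the plan says.** **ET efficacy data are collected.** Protocol 8.1 and SAP 3.1 provide for efficacy evaluations at end of treatment or ET. For a subject who withdraws consent, Protocol 8.1 says "every attempt should be made to have the subject complete the ET visit and complete the study assessments listed at Week 52".

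**The windows differ by type of data.** SAP 7.2 has one table headed "Analysis Visit Window for PtGA, PhGA, mRSS, FVC, DLco, HAQ-DI". Its rows are Screening, Baseline, Weeks 2, 6, 16, 26, 39, 52 and 56, with no ET row. The next table, headed "Analysis Visit Window for other than PtGA, PhGA, mRSS, FVC, DLco, HAQ-DI and pregnancy test", has an ET row (end of treatment to 7 days after), and so does the pregnancy-test table.

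**The choice within a window.** SAP 7.2 says that "if there are multiple data in a window, the closest data to nominal day will be used"; the later date wins only if the distances are equal. It also says, as a default, that "no data imputation will be performed using data from outside the allowable range". Protocol 16.3.2.2 words the choice differently: "then the latest and closest value of the window value will be used for analysis". SAP section 10, which lists changes from the protocol, does not mention this rule. SAP section 1 says that the SAP supersedes the protocol on statistical detail.

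**Where the values go.** SAP 8.2.1 imputes missing Week 52 CRISS under missing at random, with 50 datasets, from CRISS at the visits, treatment group and randomization stratum. Some text after the listed factors is blacked out. SAP 8.2.2 fits MMRMs to the five components without imputation.

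**The concern.** Missing at random is easier to defend when the imputation conditions on the last value seen before a subject left. The rule can remove exactly that value. A subject seen for Week 26 on Day 183 who terminates on Day 228 has both values in the Week 26 window. The Day 183 value is kept, and the value taken 45 days later is not used at Week 26, at Week 39 or in the imputation.

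If such subjects leave because they have worsened since the scheduled visit, their imputed Week 52 CRISS is too high. If more of them are in one arm, the treatment difference shifts in that arm's favour. The component MMRMs lose the same values.

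**Working it through.** **Scale of the trial.** The documents give no figure for ET data loss. The design figure used here for scale is 80% power with 36 per group, difference 0.35, SD 0.5 and two-sided alpha 0.05 (SAP 3.3). Noether's formula for the Wilcoxon test reproduces it:
- P(X>Y) = Φ(0.7/√2) = 0.690
- power = Φ(√(12 × 0.25 × 72) × 0.190 − 1.960) = 79.6%

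The standard error of a difference in means on these inputs is 0.5 × √(2/36) = 0.118.

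**Days on which the ET value is displaced.** Assume the scheduled visit took place on its nominal day. An ET after that day in the same window loses. An ET before it, with the scheduled visit not yet done, is kept as that visit's value.

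| Window (SAP 7.2) | Days | Nominal day | ET days displaced | Share |
|---|---|---|---|---|
| Week 16 | 78-147 (70) | 113 | 114-147: 34 | 49% |
| Week 26 | 148-228 (81) | 183 | 184-228: 45 | 56% |
| Week 39 | 229-319 (91) | 274 | 275-319: 45 | 49% |
| Week 52, before nominal | 320-364 (45) | 365 | 0 (ET is the Week 52 value) | 0% |

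- Days 78-319: (34 + 45 + 45) / (70 + 81 + 91) = 124/242 = 51%
- Days 78-364: 124 / (242 + 45) = 124/287 = 43%

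**Sensitivity of that share (ET timing is assumed throughout).**
- Scheduled visits spread over the protocol's ±7 days: 46% (Days 78-319) and 39% (Days 78-364).
- ET times exponential with mean 120 or 365 days, or weighted to late exits, with the same spread of visits: 37-39% (Days 78-364).
- If 25% to 50% of ETs take place at a scheduled visit, nothing is displaced for those: from 0.50 × 43% = 22% to 0.75 × 51% = 38%.

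**Number of subjects.** Dropout of 10%, 20% or 30% of 72 (assumed) is about 7, 14 or 22 subjects. At 43-51%, about 3-4, 6-7 or 9-11 of them lose their last value.

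**Size of the bias.** A simulation with an assumed exit mechanism put imputed CRISS about 0.04-0.06 too high among affected dropouts when exits follow worsening, and about zero off otherwise. The shift in an arm mean is dropout × displaced share × shift among those affected:
- 10% dropout: 0.10 × 0.43 × 0.04 = 0.002 to 0.10 × 0.51 × 0.06 = 0.003
- 20% dropout: 0.20 × 0.43 × 0.04 = 0.003 to 0.20 × 0.51 × 0.06 = 0.006
- 30% dropout: 0.30 × 0.43 × 0.04 = 0.005 to 0.30 × 0.51 × 0.06 = 0.009

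The arm-mean shift simulated directly was 0.003-0.014. The top of that range is 0.014/0.35 = 4% of the design difference and 0.014/0.118 = 0.12 standard errors.

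A harsher set of assumptions puts every exit on a displaced day and raises the exit odds 2.0- to 3.3-fold per SD of worsening, with 8-23% exits. It gives 0.09-0.22 among dropouts and 0.008-0.048 in the arm mean. If only 39-51% of exits fall on displaced days, the arm figure becomes 0.39 × 0.008 = 0.003 to 0.51 × 0.048 = 0.024.

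**The case against.** **Stands: the share is conditional.** A reader might infer that about half of all ET efficacy measurements are thrown away. The documents do not support that. The 51% needs uniform ET timing and visits on their nominal days, and it stops at Day 319, although an ET on Days 320-364 is itself the Week 52 value. Nor does the scheduled value always win. A Week 26 visit on Day 176, within its ±7 days, loses to an ET on Days 184-189 and also on Day 190, where the tie goes to the later date. ETs before Day 78 have no CRISS analysis visit because SAP 9.3 reports CRISS only from Week 16. That loss does not come from the closest-day rule.

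**Stands: exit for worsening is an assumption.** Protocol 8.1 encourages subjects who stop drug to stay to Week 52, and Protocol 11.3.1.2 lets those who take rescue therapy continue study drug. Protocol 8.2.2 reports more discontinuations for adverse events at 300 mg in an earlier Phase 2 study, but attributes the excess mainly to tolerability events. Unequal exits between arms are therefore plausible, but exits caused by worsening skin or lung disease are not established.

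**Stands: the conflict with the protocol is thin.** A reader might take the SAP to contradict Protocol 16.3.2.2. The protocol's latest-and-closest wording is ambiguous, and the SAP's rule is one reasonable reading of it. Similarly, the table that has an ET row covers all other data, not safety alone, and SAP 9.3 reports no ET visit for safety either. The missing row may be deliberate.

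**Limits what can be checked.** Part of MI Step 1 is blacked out, so the full list of imputation inputs cannot be confirmed.

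**Does not remove the point.** None of this changes what the rule does to an ET value taken after a completed visit in the same window.

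**Conclusion.** The gap is real and narrow. For subjects who leave the study after a window's scheduled visit, SAP 7.2 normally discards the CRISS components measured at ET, and both the primary imputation and the component MMRMs run without them. That is 43-51% of possible ET days under uniform timing with visits on nominal days, and about 22-46% under the other timings tried.

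A reader might go further and infer that the primary result is materially biased. The documents do not support that. Bias needs exits that follow worsening since the last scheduled visit, and it reaches the treatment difference only as far as such exits differ between arms. The arm-mean shift is about 0.01 or less in most assumed scenarios, against a design difference of 0.35. The dropout rate and the exit mechanism are assumptions, and the simulated figures are for mean CRISS, not the Hodges-Lehmann estimate. The stated sample size and power are unaffected. The reason to act is that the data are already collected and the correction is cheap.

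**What to change.** Add to SAP 7.2, under the efficacy window table:

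> *For subjects who terminate the study early, if an ET efficacy assessment falls in the same analysis window as a scheduled visit, the latest complete set of CRISS components in that window is used.*

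Use these values in MI Step 1 and the MMRMs. List the rule in SAP section 10 as the reconciliation with Protocol 16.3.2.2.

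Do not move ET values to the next scheduled visit, and do not treat an ET before Day 320 as the observed Week 52 score. Moving them would go against the SAP's default on out-of-window data. It would turn a Day 275-319 value into the primary endpoint without imputation uncertainty, and could shift a Day 2 value to Day 113 (111 days, about 16 weeks). In simulation it gave a bias of about −0.03 among affected dropouts even when exits were random.

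Keeping the latest value inside its own window cut the worsening-driven bias among affected dropouts from 0.04-0.06 to about 0.01-0.02. The cost was about +0.01 when exits were random. The retained value may lie up to 45 days after the nominal day (228 − 183, or 319 − 274), which the windows already allow. The change needs one sentence and one programming rule, no new data, and can be made before database lock. It does not address ETs before Day 78.

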8 STATISTICAL METHODOLOGY

All available data will be listed. Listings will be presented in treatment, subject, visit (where applicable), and date (where applicable) order.

8.1 Study Subjects

8.1.1 Subject Disposition

The following will be provided:

Number of screened subjects: defined as those who met the inclusion criteria regarding the target indication and signed the ICF

Number (%) of screen failures and reasons of screen failure

Number of randomized subjects: defined as those who received a randomization number

Number (%) of subjects who took the first drug

Number (%) of subjects in the ITT population

Number (%) of subjects who completed Week 52

Number (%) of subjects who discontinued the Randomized, Double-Blind Treatment Period, and the reasons for discontinuation of Randomized, Double-Blind Treatment Period

Number (%) of subjects who performed the follow-up visit

Number (%) of subjects who did not perform the follow-up visit and the reason for not performing the follow-up visit

Subject who used rescue therapy

Subject who reduced the dose

8.1.2 Analysis Populations

Number (%) of subjects of each analysis population will be summarized in the RAND population.

8.1.3 Protocol Deviations

Major protocol deviations will be summarized on the ITT population. The number and percentage of subjects with any major protocol deviation and within each deviation category will be summarized by treatment group in the ITT population.

8.1.4 Demographic and Other Baseline Characteristics

Demographic and other baseline characteristics will be summarized on the ITT population. The following demographic and other baseline characteristics will be used. Demographic and other baseline characteristics will be summarized by Placebo, MT-7117 over all, MT-7117 [REDACTED] only, [REDACTED] regimen, [REDACTED] regimen, Total.

	category	descriptive
Sex	Male, Female	
Age(years)	18 – 65 >65	Yes
Height(cm)		Yes
Weight(kg)	<45 >=45	Yes
BMI(kg/m2)		Yes
Race	White, Black or African American, Asian, American Indian or Alaska Native, Native Hawaiian or Pacific Islander, Other	
Country	USA, Canada, UK, Italy, Spain, Germany, Poland and Belguim (from IWRS data)	
Region	North America, Europe	
Ethnicity	Hispanic or Latino, Non-Hispanic or Latino, Other	
Disease Duration of SSc		Yes
SSc-ILD	Yes, No, Uncertain	
SSc-ILD based on the HRCT assessment	Yes, No, Uncertain	

Immunosuppressant and corticosteroid	Any immunosuppressant, MMF, MTX, AZA, LEF, Corticosteroid	
--------------------------------------	---	--

8.1.5 Medical History

Medical history will be summarized on the SAF population. In the above tables, SOC is sorted by International order; then within SOC, PT is sorted by descending counts under MT-7117 over all column, then descending counts under Placebo column, then alphabetic order for PTs with the same count.

8.1.6 Prior or Concomitant Medications

The prior and concomitant medications will be summarized in table separately by ATC level 2, preferred name and treatment group and presented in data listing for the SAF population.

Regarding of the concomitant medication, the dosage of the following medications which is ongoing at the time of the first dose of study drug or is started after the first dose of study drug will be descriptively summarized. Also, the duration of the medication use will be descriptively summarized. Data describing units other than "mg" or "g" will be included only in the tabulation of time period. These medication codes is attached in the Appendix 13.1. For "METHYLPREDNISOLONE" and "METHYLPREDNISOLONE SODIUM SUCCINATE", the dose multiplied by 0.8 will be used for tabulation to convert these drugs to equivalent doses of corticosteroid.

Mycophenolate (up to 3g/day)

Mycophenolic acid (up to 2.14 g/day)

Methotrexate (up to 25 mg/Week)

Leflunomide (up to 20 mg/day)

Azathioprine (up to 3 mg/kg/day)

Corticosteroid (up to \leq 40 mg/day of prednisone)

8.1.7 Prohibited Medications

The prohibited medications coded by the protocol Appendix 2 will be summarized and listed on the SAF population. The data will be coded using World Health Organization Drug Dictionary (WHO-DD). The summaries will be by ATC level 2 and preferred name and treatment.

8.1.8 Rescue Medications

The Rescue Medications will be summarized and listed on the SAF population. The data will be coded using World Health Organization Drug Dictionary (WHO-DD). The summaries will be by ATC level 2 and preferred name and period and treatment. The Rescue Medications and the reason (e.g., Worsening mRSS of a minimum of 5 points and at least 25% increase relative to baseline) to use it will be summarized by Placebo, MT-7117 over all, MT-7117 [REDACTED] only, [REDACTED] to [REDACTED] regimen, [REDACTED] to [REDACTED] regimen.

[Analysis period using the start date of the rescue medication]

Week 16 =< Period =< Week 26

Week 26 < Period =< Week 39

Week 39 < Period =< Week 52

8.1.9 Treatment Duration and Exposure and Treatment Compliance

Treatment duration and Exposure and Treatment compliance will be summarized on the ITT population.

Treatment duration (months) will be calculated by dividing by 30.4375 for treatment duration (days). Then, treatment duration months and Exposure will be summarized as a categorical variable using the following categories:

- 0 to <= 3 months
- > 3 months to <= 6 months
- > 6 months to <= 12 months
- >12 months
- [REDACTED]
- [REDACTED]
- [REDACTED]

The number and percentage of treatment compliance will be calculated using the range 80% <= compliance <= 120% as a subject being treatment compliant. The number and percentage of treatment compliance will be summarized by treatment and and following period.

- Baseline to 15 Study Day
- 16 Study Day to 43 Study Day
- 44 Study Day to 113 Study Day
- 114 Study Day to 183 Study Day
- 184 Study Day to 274 Study Day

- 275 Study Day to 365 Study Day

8.1.10 Interruption/permanent discontinuation of study drug and subject question for study medication

The number and percentage of study drug interruption and study drug permanent discontinuation will be calculated with it's reason by treatment on the ITT population. Interruption duration of study drug will be summarized by treatment on the ITT population. The number and percentage of subject question for study medication will be calculated by treatment on the ITT population.

8.2 Efficacy Assessments

All efficacy endpoints will be summarized using descriptive statistics or using the number with percentage and presented in data listing.

8.2.1 Primary Efficacy Endpoint

Primary Analysis

The primary treatment comparisons of interest are the ACR CRISS score for MT-7117 treatment group compared with placebo group at Week 52. MT-7117 treatment group includes all subjects treated with MT-7117 regardless down titrated or not. The treatment MT-7117 dose level at EOT will be compared with placebo as secondary analysis.

The primary endpoint will be summarized using descriptive statistics with interquartile range. The distribution of ACR CRISS score may not be normal distribution. For ACR CRISS score at Weeks 16, 26, 39, and 52 the comparison between MT-7117 treatment group and placebo group will be performed using the non-parametric analysis method. The point estimates and 2 sided 95% CIs and associated P-values for the difference between the treatment groups will be obtained using the Hodges-Lehman estimator corresponding to Wilcoxon's rank sum test. This non-parametric analysis will be performed with multiple imputation method, assuming missing at random. A supportive analysis will be performed at the same way for the primary endpoints using the per-protocol set (PPS). As a secondary analysis for the primary endpoint, the same analysis method will be applied to the intent to treat (ITT) population but the patients' data after taking rescue therapy will not be included. This approach will be performed to investigate a sensitivity for the primary analysis.

MI Step 1: The ACR CRISS score at week 52 will be multiply imputed using Fully Conditional Specification Method methodology under MAR assumption. The imputation for the missing ACR CRISS total score at week 52 will be conducted using all visit data of all subjects with available ACR CRISS total score up to week 52. The 50 different imputed datasets will be created using the MI procedure in SAS with 2023 for seed value. The following factors will be included in the imputation model: treatment group (TRT01P), randomization strata (the baseline autoantibody status of anti-RNA Polymerase III (positive or negative)).

[REDACTED]

[REDACTED]

[REDACTED]

[REDACTED]

[REDACTED]

MI Step 2: The imputed datasets generated with the approach described above do contain only non-missing values. Non-parametric analysis using The Hodges-Lehman estimator will be performed for ACR CRISS score on each of the 50 generated imputed datasets. The ACR CRISS score at each visit (Weeks 16, 26, 39, and 52) from two treatments groups will enter the corresponding analysis. The Location shift estimate and two-sided 95% confidence intervals will be obtained using the Hodges-Lehman estimator corresponding to Wilcoxon's rank sum test. The paired comparison between each MT-7117 dose level with placebo will also be performed using this non-parametric analysis method. The following SAS code will be used:

[REDACTED]

[REDACTED]

[REDACTED]

[REDACTED]

MI Step 3 : Finally, the MIANALYZE procedure in SAS will be applied to combine the results from these analyses to derive an overall estimate of the treatment differences at W16, ..., W52 according to the following code. In addition to the estimates, corresponding 95% confidence intervals and p-values will be calculated.

The following example SAS code will be used:

*Combine LS mean difference estimates;

[REDACTED]

[REDACTED] TDERR;
RUN;

Prespecified Subgroup Analysis

The treatment effect on the primary endpoint of CRISS score up to Week 52, the secondary endpoint of change from baseline to Week 52 in mRSS and new Revised CRISS up to Week 52 across different subgroups will be explored based on the ITT population for the following subgroups.

Baseline CRP (<6.0, >=6.0, mg/dL)

Baseline ESR (<28, >=28, mm/hr)

Baseline Platelets (<330, >=330, x10^9/L)

Baseline SSc disease duration (<=3 years, >3 and <=5)

Baseline mRSS score (<25, >=25)

[REDACTED]
[REDACTED]
[REDACTED]

Concomitant medication (MMF, no-MMF)

Concomitant medication (Immunosuppressant(IM)*, non-IM)

Baseline disease duration and concomitant medication (<2 years+MMF, <2 years+no-MMF, >=2 years+MMF, >=2 years+no-MMF)

Region (North America, Europe)

MC1R variant (number of MC1R variants, e.g. 0, 1, 2, or 3 and each MC1R variant (MC1R variant: n≥3))

[REDACTED]
[REDACTED]

Baseline %pFVC (>50% and <=80% , >80%)

*Immunosuppressant(IM): methotrexate, leflunomide, azathioprine, mycophenolate and mycophenolic acid

The impact of MT-7117 dose reduction to efficacy

Efficacy analysis of MT-7117 vs. Placebo will be basically performed based on the ITT population. In this study dose reduction due to significant intolerable AEs is allowed. If efficacy of MT-7117 [REDACTED] only, [REDACTED] to [REDACTED] regimen, [REDACTED] to [REDACTED] regimen is investigated, the randomization principle cannot be maintained so that there is comparability of these regimens. However, given this limitation, in order to investigate the potential treatment effect, the treatment effect on the primary endpoint of CRISS score up to Week 52 and the second day endpoint of change from baseline up to Week 52 in mRSS, HAQ-DI, Patient Global Assessment, %pFVC, Physician Global Assessment and Revised CRISS up to Week 52 across the following treatment regimens will be explored based on the ITT population. Then, demographic and disease characteristics specified in Section 8.1.4 will be similarly evaluated.

Treatment comparison is the following;

MT-7117 [REDACTED] only,

MT-7117 [REDACTED]

MT-7117 [REDACTED]

vs. Placebo

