13.6 Maintenance of the Study Blind and Unblinding

All study treatments will be double-blinded during the 52 weeks study; neither the subject nor the study site personnel will know which treatment is being taken. Each subject's treatment will

be provided a unique code number, traceable to the identity, dose, and batch number of the study drug. The IWRS will be used to hold treatment codes for each subject. The codes will only be accessible to authorized IWRS users.

Subjects down-titration will be processed via IWRS. Subjects in the MT-7117 300 mg treatment group will be assigned to the MT-7117 200 mg treatment by IWRS. Subjects in the MT-7117 200 mg treatment group will be assigned to the MT-7117 100 mg treatment group for the second time for down-titration. Subjects in the placebo treatment group will remain in the placebo group by IWRS.

The IWRS should not normally be accessed with a request to break the treatment code for reasons other than safety or in an emergency. Should the Investigator wish to break the code for such reasons, he/she are advised to consult the Sponsor (or designee) in advance where feasible. If this is not possible, the Investigator may access the IWRS to obtain the treatment code and provide the system with the reason for breaking the blind. The Sponsor should be notified as soon as possible thereafter. If the blind is broken for any individual subject, the subject must be withdrawn from the study, and any procedures accompanying withdrawal will be performed (Section 9.5).

The Sponsor and study team will remain blinded throughout the entire duration of the study.

An electronic list of randomization codes will be retrieved from IWRS and transferred to the Sponsor at the end of the study.

As PK analysis will only be performed on samples from subjects receiving active study drug, unblinded randomization codes will be provided to the PK laboratory.

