3.3 Sample Size and Power Considerations

The planned sample size of 72 is expected to provide power for the comparison between MT-7117 treatment group and placebo group for ACR CRISS score at Week 52. The calculation of sample size assumes a 2-sided alpha level of 0.05 and uses EAST (Version 6.5) for Wilcoxon Mann Whitney test. The randomized 72 subjects (36 subjects for MT-7117 and 36 subjects for placebo) with a 1:1 allocation ratio would provide 80% power to detect treatment difference of 0.35 (35% improvement on MT-7117 treatment group compared to placebo group) in ACR CRISS score at Week 52 with an associated standard deviation (SD) of 0.5.

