6.2 Statistical Tests

Unless otherwise specified, all formal statistical tests of treatment effects will be done at two-sided significance level of 0.05. Point estimates will be accompanied with two-sided 95% CIs where applicable.

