9.2 Treatment Groups to Report

Unless otherwise specified, the following treatment groups will be reported.

Treatment Group	For TTEs
MT-7117 [REDACTED] with dose reduction to [REDACTED]	MT-7117
Placebo	Placebo

For only CRISS score and mRSS, the following treatment groups will be reported as the secondary analysis.

Treatment Group	For TTEs
MT-7117 [REDACTED]	MT-7117 [REDACTED]
MT-7117 [REDACTED]	MT-7117 [REDACTED]
MT-7117 [REDACTED]	MT-7117 [REDACTED]
Placebo	Placebo

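### SAP 8.2.1 and 9.2 make MT-7117 dose level at EOT versus placebo a secondary analysis, while 8.2.1 also concedes that essentially the same groups are not randomised and are only explored

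*SAP*

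**What the plan says.** The primary comparison in SAP 8.2.1 pools every subject treated with MT-7117, whether or not the dose was reduced. The same paragraph adds: "The treatment MT-7117 dose level at EOT will be compared with placebo as secondary analysis". Under MI Step 2 the SAP says: "The paired comparison between each MT-7117 dose level with placebo will also be performed using this non-parametric analysis method". MI Step 3 then combines the imputed results into estimates, 95% confidence intervals and p-values. SAP 9.2 repeats the status: "For only CRISS score and mRSS, the following treatment groups will be reported as the secondary analysis".

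Later in 8.2.1, under the impact of dose reduction on efficacy, the SAP says that when the full-dose-only and reduced-dose regimens are examined, "the randomization principle cannot be maintained so that there is comparability of these regimens". It goes on with that limitation stated, describes the effect as something to be explored, and asks for baseline characteristics by regimen.

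Dose is lowered stepwise for intolerable adverse events, with no return to a higher dose (Protocol 8.1 and 10.1.3.2). On the other side of the comparison, "Subjects in the placebo treatment group will remain in the placebo group by IWRS" (Protocol 13.6). SAP 6.2 sets the level for every test: "all formal statistical tests of treatment effects will be done at two-sided significance level of 0.05". No multiplicity adjustment is stated.

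**The concern.** A rank-sum test takes its null distribution from the exchangeability of the two groups. Here one group is the MT-7117 subjects who ended at a given dose because of how they tolerated treatment. The other is all placebo subjects, tolerant and intolerant together. The hypothesis tested is therefore a joint one: no drug effect, and no relation between tolerability and CRISS.

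The documents give some reason to expect a relation. Protocol 10.1.3.2 illustrates severe events by limits on self-care such as eating, dressing and walking. These are HAQ-DI domains, and HAQ-DI enters the CRISS equation with coefficient -3.41. Both global ratings ask about overall health in the last week.

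If subjects doing worse are more likely to reduce dose, the full-dose group will look better than placebo and the lowest-dose group worse, even when the drug does nothing. In a Phase 2 proof-of-concept trial, a reader of secondary results with p-values could take that pattern as evidence of dose response.

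**Working it through.** **The plan's own figure.** SAP 3.3 gives 80% power with "The randomized 72 subjects (36 subjects for MT-7117 and 36 subjects for placebo) with a 1:1 allocation ratio", a difference of 0.35 and an SD of 0.5. "The calculation of sample size assumes a 2-sided alpha level of 0.05 and uses EAST (Version 6.5) for Wilcoxon Mann Whitney test". Noether's formula reproduces this:

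- P(X>Y) = Φ(0.35 / (0.5 × √2)) = 0.6897.
- N = (1.960 + 0.842)² / (3 × 0.1897²) = 72.7.
- Power at N = 72 is Φ(√(3 × 72) × 0.1897 − 1.960) = 79.6%.

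That calculation covers the pooled 36 versus 36 comparison only. The dose-level comparisons have no sample-size basis in the documents.

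**The two texts side by side.** Reduction is stepwise and cannot be reversed, so the dose level at the end of treatment and the regimen followed define essentially the same three groups. In the primary-analysis text, MI Step 2 and section 9.2, their comparison with placebo is secondary and uses the primary method. In the dose-reduction text it is exploratory, with randomisation conceded to be lost.

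**Are p-values produced?** The SAS code is redacted. That p-values are produced for dose levels is inferred from the wording of MI Step 2, which applies the same method, and from MI Step 3, which yields p-values.

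**Simulation under no drug effect.** There are 36 subjects per arm, and latent prognosis z ~ N(0,1) in both arms. CRISS is a monotone function of z, so its scale does not affect the rank test. Tolerability is T = ρz + √(1−ρ²)e, with e ~ N(0,1). MT-7117 subjects are sorted by T into three dose levels. Each level is tested against all 36 placebo subjects by the rank-sum test at two-sided 5%. The split and ρ are assumptions. Data are complete; the imputation and combination steps were not simulated.

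Rejection rates (%) for a 60/20/20 split, across independent runs:

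| ρ | Full dose | Lowest dose | At least one of three |
|---|---|---|---|
| 0 | about 5 | about 5 | about 13 |
| 0.2 | about 7 | 9 to 10 | 20 to 21 |
| 0.3 | about 10 | 15 to 16 | 28 to 30 |
| 0.4 | 14 to 15 | 24 to 25 | 41 to 42 |

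The middle dose rejects in about 5 to 7% for ρ from 0.2 to 0.4.

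Other splits of the 36 MT-7117 subjects at ρ = 0.3:

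| Full / middle / lowest (n) | Full dose | Middle dose | Lowest dose | At least one |
|---|---|---|---|---|
| 27/5/4 | 7.6 | 7.6 | 12.9 | 25.4 |
| 18/9/9 | 12.2 | 5.3 | 15.3 | 29.8 |
| 12/12/12 | 14.8 | 4.7 | 15.0 | 31.5 |

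With 18/9/9, 11.9 of the 12.2 points for full dose favour the drug. The model is symmetric, so a negative ρ of the same size gives the same rates with the directions reversed.

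**Multiplicity alone.** Three independent tests at 5% give 1 − 0.95³ = 14.3%. Sharing the placebo arm brings this to about 13%, the ρ = 0 row.

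**Pooled comparison.** In the same simulations, all MT-7117 versus placebo rejects in about 5% of trials at every ρ and split.

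**The case against.** The strongest reply is that the SAP already discloses the problem in the same section, proceeds with the limitation stated, and tabulates baseline characteristics by regimen. This stands. A reader might infer that the authors overlooked the loss of randomisation; the dose-reduction text shows that they did not. What remains is that the limitation is missing where the comparison is given secondary status.

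Second, the link between tolerability and CRISS is not established. CRISS uses changes from baseline, not how unwell a subject is. The events named for dose reduction are vomiting, diarrhoea, headache and hyperpigmentation, and Protocol 8.2.2 reports similar events as driving the higher rates at 300 mg in an earlier study. They may be largely drug effects with little bearing on prognosis. This also stands: neither the sign nor the size of the correlation is known. A reader might infer that the p-values are invalid whatever the truth, but at zero correlation each single test keeps about 5%.

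Third, nothing confirmatory rests on the comparison. The SAP has no testing hierarchy, so the secondary label carries no claim on alpha. This limits the severity. It does not explain why one comparison carries two labels.

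**Conclusion.** The point holds as an internal contradiction with a possible statistical consequence. SAP 8.2.1 (primary-analysis text and MI Step 2) and 9.2 give a non-randomised comparison secondary status and, by inference from MI Step 3, p-values. Another part of 8.2.1 says that randomisation cannot be relied on for essentially the same groups.

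The size depends on two quantities the documents do not give. With a 60/20/20 split and correlations of 0.2 to 0.4, false rejection runs from about 7% to 14 to 15% for full dose and from about 9% to 24 to 25% for lowest dose, with little inflation for the middle dose. With no correlation, only the three-way multiplicity of about 13% remains.

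A reader might go further and infer that a false dose-response signal is likely, or that the main result is compromised. The documents support neither. The first needs a correlation they do not state, and the primary comparison pools all MT-7117 subjects as randomised.

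**What to change.** In the primary-analysis text and MI Step 2 of SAP 8.2.1, and in 9.2, call the dose-level comparison exploratory. Repeat there, and on the outputs, the limitation already given in the dose-reduction text. Report CRISS and mRSS by regimen either descriptively or as Hodges-Lehmann estimates with intervals marked as non-randomised, without p-values against placebo. Keep all MT-7117 versus placebo as the tested contrast.

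Optionally, show placebo by blinded reduction status as a descriptive aid. Protocol 10.1.3.1 already puts the date and reason of each reduction in the eCRF. That split is not a randomised comparison either, so it does not justify a test.

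The cost is a change of wording and fewer tested columns. The sponsor gives up dose-specific p-values and keeps the estimates by regimen.
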